demonstrated decreased utilization of both appropriate and inappropriate services, including prescription drugs. HDHP plans are also associated with greater patient out-of-pocket spending for care for families with chronic conditions. Patients with asthma are at particular risk from deductible costs, as controller and rescue medications are expensive branded drugs, costing \$140-\$307 a month for some inhaled steroids and \$30-60 for CFC-free albuterol inhalers without available lower-cost generic substitutes. HSA-HDHPs have been associated with decreased adherence for medications for asthma and other chronic conditions. In survey studies, we found that families in HDHPs were more likely than those in traditional plans to report health care-related financial burden and delayed/forgone care due to cost for both adults and children. In our qualitative studies, families reported challenges understanding and using HDHPs.

**Cost-sharing required by HSA-HDHPs has the potential to exacerbate disparities in access to medications for patients with asthma.** Some studies suggest that the impact of increased cost-sharing is greater for low-income populations, who are more likely to experience delayed/forgone care due to cost in HDHPs. Low-income, Hispanic, and African-American populations are more likely to report cost-related underuse of medications and other health care, and increases in copayments for chronic medications have a greater negative impact on adherence for low-income patients. However, one of our studies found that both lower and higher-income populations experience reductions in utilization in HDHPs.

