Eligible employers are those that offer only one plan type in a given benefit year: 1) traditional HMO/PPO/POS plans (deductibles  $<\$1000$ , copayments of  $<\$50$  for most services, tiered copayments for medicines); 2) HSA-HDHPs without PDLs; or 3) HSA-HDHPs with PDLs. We will select “full-replacement” employers that replace a traditional plan with an HSA-HDHP without PDL, or replace an HSA-HDHP without PDL with an HSA-HDHP with PDL, for all employees at a given point in time; matched comparison employers will include those that keep all employees in their prior plan. Including only full-replacement employers is a key strategy used in multiple previous studies to reduce member self-selection bias. The index dates for HSA-HDHP enrollees will be the dates of the employer-mandated plan switch. Matched controls will have contemporaneous enrollment in traditional plans also mandated by their employers; index dates will be assigned to be the same as matched intervention enrollees. We will also include matched controls who remain in HSA-HDHPs without PDLs. To reduce bias due to dropout, we will censor both HDHP and control patients together when either one drops out, and weight the remaining population to retain its baseline demographic and clinical profile. We estimate that there will be 621,481 adults and 310,741 children with asthma from 2004-2017 who will meet our inclusion criteria: 18,000 asthma patients in HSA-HDHPs without PDLs, 4,222 in HSA-HDHPs with PDLs, and 910,000 in traditional plans.

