## **Predictors and Covariates**

Table 2 shows the main predictors and covariates we will use in the proposed study for propensity matching to create study cohorts (CI-1, 4-5), predicting or adjusting outcomes, or stratifying analyses. Our primary predictor variables include study period and insurance type. Study period indicates the one-year period before or up to three years after the index date. Insurance type includes: 1) HSA-HDHP without PDL; 2), HSA-HDHP with PDL; and 3) traditional plan.

Other co-variates include asthma severity in the baseline period using the HEDIS definition for persistent asthma (see above under Study Population), and using chronic oral corticosteroid therapy (180+ days in the prior year) or any use of omalizumab in the baseline year to define severe asthma. To estimate co-morbidity, we will use the well-established Johns Hopkins Adjusted Clinical Groups (ACG) scores which use ICD-10 codes in the baseline period to calculate a standardized morbidity score in a specified time period. We will measure the presence of other chronic conditions from claims data in the baseline year using the Johns Hopkins ACG system. We will also measure whether enrollees have COPD as a co-morbidity, as there can be overlap with COPD and asthma, and use of similar medications.

A unique innovation of our study is the availability of data linkages (IR-2) with consumer data from a

major credit reporting company linked to insurance claims from our data vendor, Optum. Consumer data elements include total household income, net

worth, and race/ethnicity. We will combine self-reported race/ethnicity data from credit card and loan applications with data from Optum on surname analysis for identifying Hispanic or Asian ethnic groups and geocoding to derive race/ethnicity from census data. We will also use census-based indicators for neighborhood education and poverty levels. Other variables used to propensity-match cohorts and adjust for confounding will include sex and age; state/region of residence; individual versus family plan; baseline number of outpatient visits, presence of an inpatient hospitalization, and total expenditures; employer size (number of employees); and average employer baseline expenditures per capita (CI-1, 4-5).

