**Table 2: Predictors and covariates**

| Covariate                         | Use*    | Notes  |
|-----------------------------------|---------|--|
| Study period                      | P       | Pre (1 yr pre), Follow-up (up to 3 yrs post)   |
| Insurance type                    | P       | HSA-HDHP without PDL, HSA-HDHP with PDL, traditional plan  |
| Income                            | P, M, S | Subscriber income in dollars and as a % of Federal Poverty Level (FPL) (<250%, 250-399%, >400%)  |
| Lives in neighborhood with:       |         |  |
| Low education                     | P, M    | ≥25% with less than high school education  |
| High poverty                      | P, M    | ≥10% living below poverty level  |
| Low SES                           | P, M    | Either low education or high poverty   |
| Race/ethnicity                    | P, M, S | Hispanic; Asian; Black; White; Other   |
| Persistent asthma                 | P, S    | Based on HEDIS definition  |
| Severe asthma                     | P, S    | On oral steroids or omalizumab   |
| ACG Score                         | P, M, S | For patient and mean for family; >2 signifies high morbidity                                     |
| Other chronic conditions          | P, M, S | For patient, other family members, from AHRQ Chronic Condition Indicator list                    |
| Region of residence               | M       | State classified into 9 geographic regions   |
| Sex                               | P, M    |  |
| Age on index date                 | M       | For patient; mean for adults and children in family  |
| Adult vs. child                   | P, S    | Age 18-64 vs. age 4-17   |
| Family coverage                   | M       | In a family vs. individual plan  |
| Family size                       | M       | Number sharing same insurance account  |
| Family members with asthma        | P       | Other adults, other children   |
| Number of medications             | P, M    | For baseline year, controller, rescue, other (on and off PDL); for patient, other family members |
| Outpatient visits                 | M       | For baseline year: for patient and mean for family   |
| Hospitalization                   | M       | For baseline year: ≥1 admission, mean per family   |
| Total expenditures                | M       | For baseline year: for patient and mean for family   |
| Employer size                     | M       | 2-50; 51-250; 251-999; ≥1000 employees   |

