| Employer health care expenditures | M       | Per capita, for baseline year  |

\* P=predictors; M=used in propensity matching; S=used to stratify analyses

category; baseline level and trend of total per capita health care expenditure quintile; baseline level and trend of outpatient, ED, and hospital visits quintile; median employee age; median employee ACG score; and percentage of employees who are women, in family plans, and living in lower SES neighborhoods (Table 2). We will perform this employer-level match separately for each intervention group of interest (HSA-HDHPs with and without PDLs) in order to generate each comparison with the control group remaining in traditional plans or HSA-HDHPs without PDLs.

Intervention and control groups will be matched based on their baseline characteristics when both were in the same type of plan. We will set  $p < 0.05$  as a cutoff for including predictors and use backwards selection to choose a parsimonious model, testing for significant effects on remaining predictors when one is eliminated. Following methods in our ongoing work, we will stratify employers based on resulting propensity scores into quartiles. We will then perform individual-level propensity matching within each quartile (below) to develop a multiple control groups for each intervention group.

Within employer propensity quartiles, we will create closely matched control groups using individual-level propensity score matching (CI-1, 4-5), with family-level covariates included in the matching. Using individual and family-level covariates from the baseline period, we will match four contemporaneous control group patients to each intervention group patient within a standard propensity score caliper (0.2 of the standard deviation of the logit of the pooled baseline propensity score). Use of a comparison group matched at both employer- and individual-level will generate study cohorts with nearly identical employer/member demographics and baseline health care trends, offering a further degree of control for any potential changes that may influence specific study outcomes.

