### **Methods to monitor and address missing data (MD- 1-3, 5)**

We have identified the following 5 variables as exhibiting data missingness (MD-1) in our dataset for this study:

- Variable 1: Geocoded poverty level
- Variable 2: Geocoded education level
- Variable 3: Member-level income level
- Variable 4: Member-level net worth
- Variable 5: Member-level deductible Level

**Missing poverty, education, income, and net worth data:** We will use 3 methods to accommodate missingness (MD- 2-3): (a) multiple imputation, (b) modeling missingness as a member-level characteristic, and (c) excluding members with missing data. If findings differ, we will present results using all 3 methods in manuscripts or attached appendices. We will use SAS procedures PROC MI and PROC MIANALYZE to impute the missing individual level covariates and conduct the statistical analyses under the assumption of missing at random. The SAS procedure PROC MI will impute the missing variables (including individual net worth, income level, poverty level and education level) using other available variables such as age, gender, census block level income, poverty, education etc. Then we will use PROC MIANALYZE to analyze the imputed data. We will also explore certain Bayesian imputation techniques to handle missing data in case missing is not at random and compare the results. If the degree of missingness for member-level credit report data is found to be too great, we will still be able to use geocoded poverty and education census block-level data, for which missingness has been less than 1% in the study team's prior work using this data source.

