*Hypothesis (see Figure 2): Enrollees with asthma in HSA-HDHPs without PDLs will have worse adherence to controller medications, greater need for rescue medications, and higher rates of asthma-related ED visits and hospitalizations, with widening of income and racial/ethnic disparities; the addition of a PDL will improve use of controllers and rescue medications, reduce ED and hospitalization rates, and lessen disparities.*

Analyses will compare changes in outcomes from baseline to up to three years of follow-up among 1) asthma patients switched to HSA-HDHPs without PDLs from traditional plans vs. matched patients whose employers remain in traditional plans; and 2) patients switched to HSA-HDHPs with PDLs from traditional plans vs. matched controls remaining in HSA-HDHPs without PDLs. Sensitivity analyses will compare patients switched to HSA-HDHPs with PDLs from traditional plans vs. those who remain in traditional plans to examine the combined impact of both increasing the deductible and gaining a PDL. We will use separate regression models to compare year-to-year changes for each intervention group relative to its matched control group, rather than including all patients in a single model with multiple interaction terms. For secondary analyses of enrollees in the larger set of plan types that include PDLs, we will compare enrollees who are switched from plans with no PDL to plans with a PDL vs. those who remain in plans without a PDL. These analyses will match and adjust for different baseline plan types and deductible levels.

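### In the main PDL contrast, deductible level is neither matched nor adjusted for, and nothing checks whether it changes on the date the PDL is added

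*Combined protocol and SAP*

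**What the plan says.** The Study Population section selects full-replacement employers that "replace an HSA-HDHP without PDL with an HSA-HDHP with PDL, for all employees at a given point in time"; for controls, "matched comparison employers will include those that keep all employees in their prior plan". Neither condition mentions the deductible amount before or after the index date.

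The variables used for matching and adjustment are given in Predictors and Covariates:

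- **Individual and family level:** "Other variables used to propensity-match cohorts and adjust for confounding will include sex and age; state/region of residence; individual versus family plan", followed by baseline use, spending and employer size. Deductible is not listed.
- **Employer level:** size, levels and trends in spending and visits, then "median employee age; median employee ACG score; and percentage of employees who are women, in family plans, and living in lower SES neighborhoods". Deductible is not listed.
- **Table 2**, which also supplies the model adjustment set, codes insurance type as "HSA-HDHP without PDL, HSA-HDHP with PDL, traditional plan" and has no deductible row.

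Arms are matched while both are in the same type of plan, not at the same deductible. The Background section gives only a federal minimum for HSA-qualified plans ($1300 individual, $2600 family), so levels above it can vary.

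Deductible matching appears once, in the Aim 2 analysis plan, for the secondary analyses of the wider set of plan types: "These analyses will match and adjust for different baseline plan types and deductible levels". The data are at hand. The missing-data section lists "Variable 5: Member-level deductible Level" and describes detailed benefit information for about 80% of employer groups, with a benefit-type variable or imputation for the rest.

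**The concern.** The aim is to learn what happens when asthma drugs are exempted from the deductible. An employer that adds a PDL is redesigning its benefit and may move the deductible at the same renewal. The plan has no rule or table that would reveal this. A change that starts on the index date in one arm only is not removed by full replacement (which addresses member self-selection), by two-level propensity matching (baseline differences) or by matching on baseline trends (the pre-period). It enters the insurance-type-by-period interaction, which is the effect estimate.

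The direction matters. The Background section reports that the team's earlier work associated a switch to a high-deductible plan with fewer ED visits. A deductible increase bundled with the PDL could therefore look like a PDL benefit on ED use while hiding a PDL benefit on total OOP cost. A decrease would do the reverse.

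**Working it through.** **1. Which outcomes are exposed.** Under the conceptual model and the outcome definitions, listed controllers and rescue inhalers carry no cost-sharing once the PDL is in place.

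| Outcome | Exposure to a deductible change at the switch |
|---|---|
| ED visits, hospitalizations | Direct: still under the deductible |
| Total OOP cost | Direct, through services still under the deductible |
| Controllers not on the PDL | Direct |
| Adherence to listed controllers | Mainly indirect: the prior deductible sets how large the price cut is (effect modification) |

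**2. Table 3, PDL contrast (4,222 vs 16,888; 80% power, alpha 0.05).** For OOP the detectable difference is (1.96 + 0.84) × SD × √(1/4,222 + 1/16,888). No SD is stated. Solving for $47 gives an SD of about $975, and the other OOP rows imply $958 to $989, so they agree with one another. For ED visits or hospitalizations at 8.4 per 100, I obtain 1.30–1.37% two-sided and 1.16–1.22% one-sided, against 1.2% stated. For PDC treated as a proportion at 46%, I obtain 2.40% two-sided and 2.13% one-sided, against 2.0% stated. Sidedness and SDs are not given, so the table can be neither confirmed nor called wrong. I use its figures only as a yardstick.

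**3. Size of a possible OOP bias.** To a first approximation, bias = f × h × D, where f is the share of switchers whose deductible changes, h the share of those who spend through the change, and D the dollar change. None of the three is in the documents; all are assumptions.

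- D = $250, f = 10%, h = 20%: $5
- D = $500, f = 25%, h = 40%: $50
- D = $1000, f = 50%, h = 60%: $300

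The product f × h that makes the bias equal to $47 is 47/250 = 18.8%, 47/500 = 9.4% or 47/1000 = 4.7%.

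**4. Consequence for inference.** With SD $975 the standard error is 975 × √(1/4,222 + 1/16,888) ≈ $16.8. If the PDL truly had no effect on OOP cost, a two-sided 5% test would be significant about 12% of the time at a bias of $12.50, 32% at $25 and 80% at $47.

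**5. A related inconsistency.** The Aim 2 analysis plan describes the second main comparison as patients moving from traditional plans to HSA-HDHPs with PDLs, against controls staying in HSA-HDHPs without PDLs. The study overview and Study Population sections have both arms start in HSA-HDHPs without PDLs. Read literally, the Aim 2 wording builds a deductible change into the intervention arm. These sections must be reconciled.

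**The case against.** The strongest reply is that no harm is shown, and several stronger readings do fail.

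- **A reader might infer that the PDL estimate is biased.** The documents never say that deductibles move when a PDL is added. The OOP figures above run from $5 to $300 depending on what is assumed, so a value near $47 proves nothing.
- **A reader might treat a different but stable deductible in the controls as confounding.** Difference-in-differences largely removes a constant difference, and the arms are matched on baseline spending, use and family coverage. What remains is effect modification.
- **A reader might think controller adherence is contaminated.** Listed drugs are exempt after the switch, so a higher deductible cannot change their price, and only a few less commonly used controllers are off the list.
- **A reader might compute how long full price lasts.** At the Background section's $140 to $307 a month, filling every month uses up $1300 in 9.3 to 4.2 months (1300/140; 1300/307). That describes the price before the PDL or in controls; it does not measure bias from a deductible change.
- **A reader might say the secondary analysis controls price better.** The main contrast controls price partly by restriction, since both arms start in HSA-qualified plans. The secondary set mixes plan types and so needs the adjustment more.
- **A reader might want the unchanged-deductible subset as the headline.** The plan frames the intervention as being switched, which is a legitimate effect of the plan change as implemented. The restriction also selects on something that happens at the index date and costs precision.

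These points limit the size and reach of the concern. They do not answer the gap itself: a deductible change at the switch would go unseen and would be credited to the PDL.

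**Conclusion.** The point holds as an unchecked co-intervention in the main PDL contrast. It bears mainly on ED visits and hospitalizations, total OOP cost and off-list controllers. For listed controllers, baseline deductible matters chiefly as an effect modifier. The size is unknown. As illustration only, a $500 change needs f × h of about 9.4% to match the $47 detectable OOP difference, taking Table 3 at face value. The conclusion rests on the absence of any deductible term or rule in the main contrast, not on evidence that deductibles moved. It warrants an addition to the plan, not a new primary analysis.

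**What to change.** 1. Add baseline deductible level, together with individual or family coverage, to the matching or propensity variables for the main PDL contrast, as the plan already does for the secondary analyses.
2. Tabulate the change in deductible from before to after the index date, by arm. This costs no sample and would show whether the problem exists.
3. Pre-specify a sensitivity analysis of the PDL contrast limited to matched sets with an unchanged deductible, or adjusted for the change. Use actual amounts for the roughly 80% of employers with detailed benefit data. The imputed $1000–$2499 band would class a move from $1500 to $2000 as no change.
4. If the results differ, describe the main estimate as the effect of the plan change as implemented, not of the PDL alone.

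**Cost.** The main analysis keeps its sample apart from any sets lost to the tighter match. In the restricted analysis, detectable differences grow by 1/√r if a share r of switchers remains (r is an assumption):

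| r | Switchers | PDC | ED/hospitalization | OOP |
|---|---|---|---|---|
| 75% | 3,166 | 2.3% | 1.4% | $54 |
| 50% | 2,111 | 2.8% | 1.7% | $66 |

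The plan hypothesizes a 1–4% increase in fills, so the loss is material if many switchers drop out. That is a further reason to keep this as a sensitivity analysis.

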### **Description of Comparators (RQ-5)**

This project will assess the impact of the "intervention" of being switched to an HSA-HDHP with a PDL, relative to a control group that was not switched and remained in an HSA-HDHP, and of being switched to an HSA-HDHP without a PDL relative to a control group that was not switched and remained in a traditional plan. Comparator groups include:

**HSA-HDHP with PDL:** enrollment in an HSA-qualified HDHP with a PDL that exempts asthma controller and rescue medications from the deductible, after being switched by an employer from an HSA-HDHP without PDL or from a traditional plan. There is limited data on the effectiveness of HSA-HDHPs with PDLs on asthma outcomes, despite an estimated prevalence of 19% among HSA-HDHP enrollees based on the national health plan to be studied. Other VBID programs have shown modest increases in adherence to chronic medications.

**HSA-HDHP without PDL:** enrollment in an HSA-qualified HDHP without a PDL, after being switched by an employer from a traditional plan. Those who enroll in HSA-HDHPs without PDLs and do not switch will also be used as a control group for those who switch from HSA-HDHPs without PDLs to HSA-HDHPs with PDLs. Evidence in adult populations suggest a reduction in adherence to asthma medications for those enrolling in HSA-HDHPs without PDLs. In 2015, the prevalence of HSA-HDHPs among covered workers was 15%.

**Traditional plan:** enrollment in a plan with no or a low (<\$500) deductible through an employer who offers only one plan. Fifty-four percent of covered workers have traditional plans, with a baseline proportion of days covered (PDC) for asthma medications of 46%.

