For **Aims 2-4**, the study population will be drawn from 14 years of data from a large U.S. commercial health plan with membership in all 50 states and annual enrollment of ~30 million members. The eligible population will consist of adults aged 18-64 years and children aged 4-17 years with asthma in a baseline year while insured in a traditional plan; all subjects must have continuous insurance coverage with pharmacy benefits for at least 24 consecutive months. Study subjects must have spent a year in a traditional health plan with no or low deductibles prior to the switch to an HSA-HDHP without a PDL, or have spent a year in an HSA-HDHP without a PDL before switching to an HSA-HDHP with PDL, and then remain enrolled for at least one-year post-switch. Control group members spend a year in a traditional plan or a HSA-HDHP without PDL then remain that plan for at least another 12 months. As study groups for secondary analyses, we will also identify enrollees switching from traditional plans to HSA-HDHPs with PDLs for comparison with those remaining in traditional plans. We will also identify enrollees with other plan types, not just HSA-HDHPs, which appear to have PDLs in that they have lower cost-sharing for asthma medications compared to other non-preventive medications. Based on preliminary findings from qualitative interviews as part of Aim 1 of the project, we have learned the cost of asthma medications is a problem not only for enrollees in HSA-HDHPs but in other types of HDHPs and in traditional plans with low deductibles as well, so we will also identify enrollees who are switched from having no PDL to having a PDL. Each of these groups will be matched with controls who start in the same type of plan and remain in that type of plan without gaining a PDL.

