Asthma controller medications are intended to be taken regularly, so we will examine controller medication adherence using ITS. We will test the statistical significance of level or trend changes following insurance plan type switch using GLM models, adjusting for seasonality and first-order autocorrelation between sequential monthly measurements using the empirical sandwich estimator. Our analytic model will compare the odds ratio of having the primary therapy in the category available each day before and after the coverage switch. Our key independent variables will be: month, period (before or after the benefit switch), and month after the plan switch, adjusting for the same covariates as above. In addition to modeling changes in adherence to controller medications generally, we will address the variation across health plans in the types of controller medications included in PDLs by conducting sub-analyses to examine changes in adherence to the specific controller medications that are included in the PDL and those that are not included in the PDL (Aerospan, Arnuity ellipta, Asmanex HFA, Aerobid, Azmacort). For patients using medications that are not included in the PDL, we will examine the degree to which patients change to medications that are included on the PDL.

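### In the PDL contrast, controls are not aligned with switchers on benefit-year start or time in the HSA-HDHP; this can bias the ITS level change and, through tenure, the annual difference-in-differences.

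*Combined protocol and SAP*

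**What the plan says.** Study Population (PC-2) fixes the intervention date: "The index dates for HSA-HDHP enrollees will be the dates of the employer-mandated plan switch". For controls in traditional plans, "index dates will be assigned to be the same as matched intervention enrollees". The next sentence adds the controls for the PDL contrast without a rule of their own: "We will also include matched controls who remain in HSA-HDHPs without PDLs".

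The prior-plan requirement is a minimum with no cap. Switchers must "have spent a year in an HSA-HDHP without a PDL before switching to an HSA-HDHP with PDL"; for controls, "Control group members spend a year in a traditional plan or a HSA-HDHP without PDL then remain that plan for at least another 12 months". Description of Comparators (RQ-5) says where the PDL controls come from: "Those who enroll in HSA-HDHPs without PDLs and do not switch will also be used as a control group".

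The employer-level propensity list in Predictors and Covariates includes "baseline level and trend of outpatient, ED, and hospital visits quintile; median employee age; median employee ACG score", together with employer size, expenditure level and trend, sex, family coverage and neighbourhood SES. Table 2 gives the individual and family variables. Renewal month, benefit-year start and HSA-HDHP tenure appear in neither.

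In the Analysis plan (Aim 2), controller adherence is examined by ITS. Level and trend changes are tested, with month, period and month after the switch as time terms, "adjusting for seasonality and first-order autocorrelation between sequential monthly measurements". The form of the seasonality adjustment is not given.

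**The concern.** Under an HSA-HDHP without a PDL, controllers fall under the deductible, so use may be low just after a reset and higher once the deductible is met. A switcher's index date is the employer's plan change, presumably the start of a benefit year. A control whose employer renews in another month has its reset inside the windows, not at the index date. It then does not show the reset that the switcher would have had at that point without the PDL, and the ITS level change absorbs the difference.

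Tenure is a separate route. The plan expects adherence to fall after entry to an HSA-HDHP. If one arm's baseline year is more often the first HDHP year, that arm has more of the fall still to come, and the annual comparison counts it as a PDL effect. The sign depends on which arm is newer.

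The effect sought is small. Hypothesized Effect Size gives a PDL gain of 1-4%, stated in fills rather than PDC, and Table 3 gives a detectable PDC difference of 2.0%.

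**Working it through.** **Yardstick.** Table 3 gives 2.0% for 4,222 against 16,888 at 80% power and alpha 0.05. With a continuous PDC, two-sided, the detectable difference is (1.960 + 0.842) × SD × √(1/4,222 + 1/16,888) = 2.802 × SD × 0.01721. A result of 2.0% needs SD of about 0.415, which the plan does not state. Treating 46% as a binary rate gives 2.40% instead. The 2.0% is used here only as a scale and is not disputed.

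**Reset, ITS.** Assumptions: no true effect, a linear within-year PDC rise of A points that repeats each year, 12 months before and 12 after index, and no seasonality terms. Each arm is fitted with intercept, month, period and month after.

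- Switcher without the PDL, reset at index: the pre-index line extrapolates to A/2 + A/11 at index and the post-index line starts at -A/2. The level change is -12A/11, or -2.18 points for A = 2.
- Control reset shifted by 3 or 9 months: fitted level change +0.29. Difference: -2.18 - 0.29 = -2.47.
- Control reset shifted by 6 months: fitted level change +1.11. Difference, before rounding: -3.30.
- Control aligned: difference 0.

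| Within-year swing | All controls off-phase | 25% off-phase (× 0.25) |
|---|---|---|
| 2 points | -2.47 to -3.30 | -0.6 to -0.8 |
| 4 points | -4.94 to -6.59 | -1.2 to -1.6 |

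Calendar-month terms shared by both arms cancel in the between-arm difference, so they leave these figures unchanged when arms share an index month.

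**Reset, annual difference-in-differences.** Each 12-month window holds one full cycle whatever its phase, so the bias is 0 in every case above.

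**Tenure, annual difference-in-differences.** Bias = r × F × d in absolute size. F is the total fall after HDHP entry, r the share of it falling between the first and second HDHP years, and d the between-arm difference in the proportion whose baseline is the first HDHP year. Members further on are taken as stable. F is the hypothesised 5-9%; r = 0.25 is an assumption.

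- F in percentage points, d = 1: 0.25 × 5 = 1.25 and 0.25 × 9 = 2.25, so about 1.3-2.3 points.
- F relative to the 46% baseline: 0.46 × 5 = 2.3 and 0.46 × 9 = 4.14 points. A quarter gives 0.6-1.0 points.
- Partial imbalance scales with d: at d = 0.25 the first range becomes about 0.3-0.6 points.

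As a check on r, an exponential adjustment with half-life 1 to 12 months, all switchers in their first HDHP year and controls two years further on gives 0.59-1.90 points for a 5-point fall and 1.06-3.42 for a 9-point fall. With 25% of switchers in their first year, the smallest value is 0.15.

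**The case against.** The strongest reply is the plan's trend matching. Overview of Study Protocol, Study Population and Generalizability and Limitations all describe matching on baseline level or trend, and an off-phase or longer-tenured control should show a different baseline path. This stands as intent. However, the only trends listed are for expenditure and visits. For controllers, Table 2 has a baseline-year medication count and no PDC trend.

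Second, controllers are free under the PDL, so the switcher has no controller-price reset after index. That is correct. The bias comes from the reset missing in the off-phase control, relative to what the switcher would have shown without the PDL. It follows that, under this cycle, the reset can only mask a PDL benefit. A reader might infer that it could manufacture one; the calculation does not support that.

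Third, the Analysis plan uses difference-in-differences to convey effect estimates, and those are untouched by a stable reset cycle. This also stands. The reset exposure is confined to the ITS level test, which the plan nevertheless says it will carry out for controller adherence.

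Fourth, the reset figures depend on the model. With 36 follow-up months, the 25% off-phase figure falls to -0.43 to -0.58 points. With one common index month, arm-specific calendar-month terms and at least 24 follow-up months, it is 0. Since the form of the seasonality adjustment is not given, neither outcome can be assumed.

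Finally, the copied-date sentence concerns traditional-plan controls. Applying it to HSA-HDHP controls is an inference, though no other rule is stated.

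**Conclusion.** The gap is real: nothing listed aligns the two PDL arms on benefit-year start or on time in the HSA-HDHP. Its size is conditional. The within-year swing, the off-phase share, the second-year share of the fall and the tenure split are all assumptions, and the documents give no distribution of renewal month or tenure.

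Two stronger readings are tempting. One is that resets and adjustment do fall at different points in the two arms. The documents show only that they can; if most employers renew in the same month, the reset part shrinks. The other is that the whole PDL estimate is compromised by resets, which the zero bias in the annual comparison rules out while the cycle is stable.

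Tenure is the more important part because it reaches the annual estimate and is not reduced by common renewal months. At complete imbalance its size is comparable with the 2.0% detectable difference when the 5-9% is read as points, and about half that or less when read as relative.

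One passage makes it worse. The second Aim 2 comparison in the Analysis plan has PDL switchers coming from traditional plans while their controls remain in HSA-HDHPs. Read literally, this builds the tenure imbalance in: switchers have no HSA-HDHP time at index and controls have at least a year. It conflicts with Overview of Study Protocol and Study Population.

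**What to change.** For the PDL contrast:

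1. State the index-date rule for HSA-HDHP controls.
2. Match preferentially on control benefit-year start month equal to the switcher's index month, and on HSA-HDHP tenure at index (12-23, 24-35, 36+ months).
3. Where too few such controls exist, keep the remaining controls and put tenure in the propensity model.
4. Add plan-year-month terms (from each employer's own renewal month) and tenure terms to the ITS and difference-in-differences outcome models.
5. Report the distributions of renewal month and tenure by arm.
6. Reconcile the second Aim 2 comparison with Overview of Study Protocol and Study Population.

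**Cost.** The work is a few more variables, drawn mainly from enrolment and benefits data the plan already intends to use. Detailed benefit information covers only about 80% of employer groups, and renewal month is not named as a field. Strict exact matching is not advised: 16,888 controls are sought from about 18,000 members (94%), so there is little slack. Where fewer than four controls are used, precision falls. Scaling Table 3's 2.0% by variance gives 2.0 × √(1.5/1.25) = 2.2% at 2:1 and 2.0 × √(2/1.25) = 2.5% at 1:1. Preferential matching with model terms should keep most of the loss below that.
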